**MECHANISMS AND PHENOTYPES OF
HYPERTENSION IN PATIENTS IN
CHRONIC HEMODIALYSIS**

NCT06764277

DATE: 09/11/2025

STUDY PROTOCOL

 SALUD SECRETARÍA DE SALUD	Instituto Nacional de Ciencias Médicas y Nutrición Salvador Zubirán	 INSTITUTO NACIONAL DE CIENCIAS MÉDICAS Y NUTRICIÓN SALVADOR ZUBIRÁN	

Title				
Mechanisms and Phenotypes of Hypertension in Patients in Chronic Hemodialysis				
Number				
Clinical Trials.gov protocol NCT06764277.				
Investigation type				
Observational transversal studies of mechanisms, markers (diagnostic/predictive) and prevalence of phenotypes in patients in chronic hemodialysis Population (one) 1 (categorized by severity of hypertension in 3 groups: normotensive, prehypertensive, hypertensive) Study: Prospective, observational, unicentric, Open				
Investigators				
INVESTIGATOR	Institutional position	Role in the project	Telephone (ext.)	Correo-E
[name] [name]	Staff member, Dept of Nephrology and Mineral Metabolism	Principal Investigator		[contact]
[name] [name]	Staff member, Dept of Nephrology and Mineral Metabolism	Investigator	[name]	[contact]
Dra. [name]	Staff member, Dept of Nephrology and Mineral Metabolism	Investigator	[name]	[contact]
[name] [name]	Staff member, Dept of Nephrology and Mineral Metabolism	Investigator	[name]	[contact]
Dra. [name]	Bioimpedance Dpt.	Investigator	[name]	[contact]
Note. 2 new co-investigators added: [name] (Nephrology resident) and [name] (nephrology resident)				
Investigators experience and role in the investigation				
Investigator	Previous research experience			
[name] [name]	Research experience in nephrology and hypertension			
[name] [name]	Research Experience in nephrology and renal replacement therapy			
Dra. [name]	Research Experience in nephrology and renal replacement therapy			
[name] [name]	Nephrology resident			

Dra. [name]	Research experience in bioimpedance
Institution	
Instituto Nacional de Ciencias Médicas y Nutrición Salvador Zubirán.	Approved the project Yes (protocol NMM 4512-23-24-1)
Sponsorships of other institutions	
No _____	
Payment to investigators (other than employment in the institution)	
No .	
Abstract/Summary	

Title: Mechanisms and Phenotypes of Hypertension in Patients in Chronic Hemodialysis
 
Justification. Cardiovascular complications associated to arterial hypertension are critical determinants of the mortality of patients in chronic hemodialysis. Identification of the activity of the renin-angiotensin system and immune reactivity in association with water overload is of clinical importance because they are potentially treatable.
 
Aims. To examine systemic arterial blood pressure ambulatory blood pressure monitoring (ABPM) in the interdialytic period and its relation to the activity of the renin angiotensin system, immune reactivity and interdialytic weight gain in patients in chronic hemodialysis.
 
General design. Prospective study of a cohort of patients in the chronic hemodialysis program in the Instituto Nacional de Ciencias Médicas y Nutrición Salvador Zubirán. Patients with the inclusion criteria will be evaluated with ABPM during the 24 hours in the interdialytic period. Weight, blood pressure, dialysis characteristics will be recorded. Blood samples will be obtained for hormonal determinations and immune reactivity at the end of the interdialytic period. Ultrasound will be used for determination of cardiac output and central venous pressure. Systemic vascular resistance will be calculated. Electric bioimpedance will be obtained would be obtained the first post dialysis day of the long interdialytic interval. *
	

 • Note: bioimpedance was not obtained and was not part of the study 	
Background.	

Chronic kidney disease (CKD) is associated with arterial hypertension (AHT). AHT is more frequent in renal vascular disease, diabetic nephropathy and polycystic kidney disease ¹, the incidence of AHT in end stage CKD (eGFR<10ml/min/1.73m²) of any etiology is over 90% ². In CKD patients the etiology of AHT is multifactorial and sodium retention and volume expansion ^{3,4}, overactivity of the renin angiotensin system ⁵, proinflammatory immune reactivity ⁶⁻⁹, endothelin system ^{10,11}, the sympathetic nervous system¹², secondary hyperparathyroidism¹³, reduced kallikrein/kinin ¹⁴ and endothelial cell dysfunction and nitric oxide reduction¹⁵, are known to play a role.
 
In the patient with end stage CKD, the most important prohypertensive factor is sodium and water retention with extracellular volume expansion that results in increase in cardiac output and peripheral vascular resistance¹⁶. For this reason, the universally accepted therapeutic measure is to attempt to keep in the so-called dry weight ¹⁷. The determination of “dry weight” is controversial and in addition to absence of clinical signs of vascular congestion,
 
bioimpedance determinations have been used to estimate subclinical overhydration but its use has been associated with higher risk of dialysis hypotension and clinical determination of the lowest weight that is not associated with postural and dialysis hypotension or cramps and malnutrition ^{18,19,20}.
 
With the emphasis placed in overhydration as a cause of AHT in end stage CKD, not enough attention has been placed to other factors which may play an important role especially because there is no predictable correlation between the severity of overhydration and the severity of hypertension, patients with normal blood pressure have significant overhydration and patients with bioimpedance-determined dry weight may
	

have significant hypertension. It is our rough estimate that in 85-90% of patients in chronic hemodialysis hypertension is associated to volume overload without predictable correlation and 10-15% of the patients have normal blood pressure despite various degrees of water overload.

The purpose of the study is to evaluate factors that may importantly contribute to hypertension in chronic dialysis patients; in particular, the renin-angiotensin system (RAAS), the sympathetic nervous system and inflammatory immune reactivity. In relation to the RAAS, Neuman et al.²¹, found that basal levels of angiotensin II are higher in patients with CKD than in normal controls, but the reduction resulting from volume expansion is normal, indicating that physiologic responses are normal. We also know from the studies of Shalekamp et al.²² that the activation of the renin-angiotensin system in CKD is not uniform and there are patients with normal and patients with high renin activity. In relation to inflammatory reactivity generated by autoimmune mechanisms, studies of several groups including ourselves^{6,7,23,24} have established the inflammation in the arterial wall, in the central nervous system and in the kidney play an important pathogenic role by reducing vasodilatory responses that may be corrected with T regulatory cells²⁵, increasing the activity of the sympathetic nervous system²⁶⁻²⁸, inhibiting pressure natriuresis²⁹ and stimulating sodium reabsorption^{30,31}. If these findings are shown in dialysis patients it is possible that anti-inflammatory treatment could have anti-hypertensive effects as it has been shown in experimental models and in patients³².

An important aspect is the relationship between interdialytic weight gain and the phenotypes of arterial hypertension (sustained hypertension, diurnal and nocturnal hypertension, normal nocturnal dipping, non-dipping, exaggerated dipping and reverse dipping) that may be evaluated with ambulatory blood pressure monitoring (ABPM)³³ that are associated with worse prognosis^{34,35}. Of interest, there are significant differences between ABPM and pre and post-dialysis blood pressure that are worthy to examine. and there is a high incidence of non-dippers in patients with CKD³⁶ and in patients with inflammation³⁷⁻³⁹.

Hypothesis and research questions.

What is the relative importance of the renin-angiotensin system, the inflammatory immune reactivity and water overload in the interdialytic blood pressure in dialysis patients?

Working hypothesis: In patients in chronic dialysis the activity of the renin-angiotensin system and the inflammatory reactivity play a critical role in the severity of hypertension and in the absence of nocturnal dipping of blood pressure

Outcomes.

Primary Outcome :

Determine the relationship of blood pressure determined by ambulatory monitoring (ABPM) in the interdialytic period and the interdialytic weight gain and the levels of angiotensin II and inflammatory markers in patients in chronic dialysis.

Secondary Outcomes:

- 1) Determine the relationship of other parameters relevant to blood pressure pathophysiology with interdialytic weight gain and blood pressure
- 2) Evaluate the relationship between interdialytic weight gain, and other variables under study with hemodynamic parameters (systemic vascular resistance and cardiac output).
- 3) Evaluate differences between ABPM and dialysis blood pressure.

Methods. .

General

- Design of the study: One cohort. Observational prospective study.
- Patients: Patients in the chronic hemodialysis program in the Instituto Nacional de Ciencias Médicas y Nutrición “Salvador Zubirán” that meet the inclusion criteria and sign informed consent
- Date. abril 2023– junio 2024

- Days and hemodialysis and hemodialysis prescription will not be modified in the study. .
- Ambulatory blood pressure monitoring will be started after dialysis when the patient will be fitted with the equipment for ambulatory blood pressure monitoring and receive the instructions for its use.
- Blood samples (10 ml) will be taken at the end of the interdialytic period, (prior to the next dialysis) for the biomarkers under study.
- 1-2 hours after the end of dialysis the determination of cardiac output and central venous pressure determinations for calculation of the peripheral vascular resistance will be done by experts with experience in ultrasound methodology.

Methods

Hemodynamic determinations. Cardiac output will be measured by experts with experience by transthoracic echocardiography using ultrasound equipment Siemens Acuson P500 with convex transducer of 2-5Mhz and lineal transducer of 7.5Mhz. Measurements will be done in the 4th intercostal space at the mid clavicular line. Cardiac output (systolic volume x heart frequency) will be determined by ultrasound doppler of the flow of the outlet of left ventricle and the aortic area.

Ambulatory blood pressure monitoring will be done with Space Lab ambulatory monitor (SpaceLabs Co) with cuffs appropriate for the patient's size starting after dialysis. Measurement will be programmed to be taken every 30 minutes during the day and every hour when the patient goes to bed. The patient will bring the equipment to the hospital when he comes for the next dialysis.

Biometric Bioimpedance. It was impossible to coordinate bioimpedance determinations within one week of the studies and this part of the study was omitted.

Blood samples and laboratory determinations. Blood samples (10 ml) will be taken from the venous side of the vascular access before the beginning of dialysis (end of the interdialytic period) and allowed to coagulate at 2-4°C. Serum samples will be stored at -80°C until the time of assay. All determinations will be done in the research laboratory of the Dept. of Nephrology and Mineral Metabolism of the Instituto de Ciencias Medicas y Nutrición "Salvador Zubirán". Angiotensin II will be determined by ELISA (my BioSource Cat.# MBS703599); Norepinephrine by ELISA (ABCAM, Cat. # AB287789); Copeptin by ELISA (Biotechne/NovusBiological, Cat, # NBP2-69822), TNF α by ELISA (Human TNF-alpha Quantikine HS ELISA, R&D systems, Cat.# HSTA00E). All laboratory determinations will be done following the instructions of the commercial supplier. Peripheral white cell counts were used to calculate the NMLR (neutrophils + monocytes /lymphocytes ratio) inflammation index.

Informed Consent.

Presented separately

Medical Intervention

None. Is an observational study.

Sample size

All the patients in the chronic hemodialysis program of the INCMNSZ that meet the inclusion criteria will be invited to participate.

Inclusion criteria

- 18 years of age or older
- More than 3 months in chronic dialysis
- Stable clinical conditions with no evidence of infection or treatment changes in the previous month

- Signed informed consent to participate in the study.

Exclusion Criteria

- Previous nephrectomy
- Participation of the patient in another clinical trial requiring interventional treatment
- Patients with prosthesis and pacemakers
- Incapacity of placement of ABPM or insufficient valid recordings
- Incomplete collection of data
- Voluntary withdrawing of informed consent

Statistical Analysis. .

Gaussian (normal) distribution will be evaluated with Kolmogorov-Smirnoff tests. Data will be expressed with mean and standard deviation or standard error of the mean and 95% confidence interval. Variables with not normal distribution will be expressed with median and interquartile range. Categorical variables will be expressed as frequencies and percentages. Comparisons between two groups with normal distribution will be done with t tests and between several groups with one way ANOVA with Tukey post-tests. Comparisons in groups that do not have a normal distribution will be done with Kruskal-Wallis tests. Correlations will be explored with Pearson (data with normal distribution) or Spearman (data with not normal distribution). Normality of log2 data distribution will be explored when obtained data do not fit with a normal distribution. Statistical calculations will be done with software STATA (Statistic Data Analysis version 14.1 or with Graphpad 10 program. Two-tail p values <0.05 will be considered significant.

Groups.

There is one population of patients and for the purpose of some analyses, patients will be categorized in 3 groups by their mean ambulatory systolic blood pressure (ABP-SBP) : 1. ABP-SBP <130 mmHg (normotensives); 2) ABP-SBP 130-139 mmHg (prehypertensives) and 3) ≥140 mmHg (hypertensives)

Mechanisms for assignation of treatments.

There will be no treatment assigned as part of the study

Recruitment potential

We aim to recruit all patients that meet the inclusion criteria. Our estimate is 40-45 patients from a total of 50-55 in the chronic hemodialysis program of the INCMNSZ.

Recruitment incentives.

There will be no incentives.

Therapy

There will be no therapy as part of the study. Treatment received by the patient will not be modified.

Retirement of participants

Premature retirement of a participant could occur at the patient's request or by the unexpected development of fever or adverse event during the study. Cause of retirement will be duly recorded

Samples, administration and monitoring of the study.

Samples will be used only for the purposes of the study. The study will be conducted or supervised by one of the investigators. Any adverse event will be immediately notified to the treatment physician.

Investigates will meet every month to discuss the progress of the study.

Methods of contacting the participants

Patients will be contacted when they come to their regular hemodialysis treatment. As specified in the informed consent, the patients will have telephone access to the following investigators [name]

([name]), [name] ([name]), [name], ([name] [name])
Risks.
This is an observational study that does not include invasive studies. The patient will receive explanation on the procedure of ABPM. Ultrasound studies are routinely used in patients in chronic dialysis
Expected benefits.
There will be no direct benefits for the patient. Knowledge of heart function and hypertension phenotype may have indirect benefits for the indication of treatment by his/her treatment physician to whom the results of the study will be available. The patient will not be charged by any of the studies
References

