# **MECHANISMS AND PHENOTYPES OF HYPERTENSION IN PATIENTS IN CHRONIC HEMODIALYSIS**

**NCT06764277**

**DATE: 09/11/2025**

**STATISTICAL ANALYSES**

### **Statistical analyses.**

All statistical analyses will be performed using GraphPad Prism version 10. The normality of data distributions was assessed using the Kolmogorov–Smirnov test. For comparisons between two groups, unpaired Student's t-tests will be applied when data followed a normal distribution, and the Mann–Whitney U test will be used for non-normally distributed data. For comparisons among more than two groups, one-way analysis of variance (ANOVA) will be performed for normally distributed data, followed by Tukey's post hoc test. When data did not meet normality assumptions, the Kruskal–Wallis test will be used, followed by Dunn's post hoc test for multiple comparisons.

For all analyses, two-tailed p-values  $< 0.05$  will be considered statistically significant. The assumptions underlying parametric tests (normality and homogeneity of variances) will be verified prior to analysis; if assumptions were not met, appropriate non-parametric alternatives will be used as described above.

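### The research question asks for the relative importance of three factors, but neither document plans an analysis that considers them together, and the SAP omits the correlations

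*Protocol*

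**What the plan says.** - **Protocol, Hypothesis and research questions.** The question is "What is the relative importance of the renin-angiotensin system, the inflammatory immune reactivity and water overload" for interdialytic blood pressure. The working hypothesis gives the renin-angiotensin system and inflammation a critical role in the severity of hypertension "and in the absence of nocturnal dipping of blood pressure".
- **Protocol, Primary Outcome.** The aim is the relationship of ambulatory blood pressure with "the interdialytic weight gain and the levels of angiotensin II and inflammatory markers".
- **Protocol, Statistical Analysis.** t tests, one-way ANOVA with Tukey tests and Kruskal-Wallis tests are planned for groups. For continuous measures, "Correlations will be explored with Pearson (data with normal distribution) or Spearman (data with not normal distribution").
- **Protocol, Groups.** The three blood pressure categories have a limited purpose: "for the purpose of some analyses, patients will be categorized in 3 groups by their mean ambulatory systolic blood pressure".
- **Protocol, Recruitment potential.** "Our estimate is 40-45 patients from a total of 50-55 in the chronic hemodialysis program".
- **SAP, Statistical analyses.** It opens with "All statistical analyses will be performed using GraphPad Prism version 10". It then names t and Mann-Whitney tests for two groups. For three or more it says "For comparisons among more than two groups, one-way analysis of variance (ANOVA) will be performed for normally distributed data", with Kruskal-Wallis and Dunn tests otherwise. It names no correlation.

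Neither document mentions regression, partial correlation, adjustment for other variables or any measure of relative importance.

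**The concern.** Relative importance is a comparative question: how much does each factor contribute, given the others? A Pearson or Spearman coefficient looks at one factor at a time. If interdialytic weight gain, angiotensin II and inflammation are related across patients, each simple correlation mixes a factor's own contribution with what it shares with the others. A real contributor can be hidden, or a factor with no contribution of its own can appear to matter.

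The protocol's background gives reason to expect some relation: it describes angiotensin II falling with volume expansion, and inflammation affecting sodium handling. These are physiological statements. They do not fix the value, or even the sign, of a between-patient correlation.

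The SAP raises a second issue. Someone working from it alone would find no analysis of the continuous relationship named in the primary outcome. If group tests were used instead, power would fall in an already small cohort.

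**Working it through.** The plan has no power or effect-size figure to reproduce; 40-45 is a recruitment estimate. From the documents I take n = 42 (within 40-45) and two-sided alpha 0.05. Every effect and correlation below is an assumption, shown over a range. Variables are standardised.

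**1. Two real contributors.** Weight gain and angiotensin II each have own effect b = 0.4 and correlate at ρ. Inflammation has effect b₃ = 0 or 0.2 and is unrelated to both.

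- Simple correlation: r = b + ρb = 0.4(1 + ρ).
- Its power: Φ(atanh(r)·√(n − 3) − 1.96), plus a negligible other tail. Example at ρ = -0.5: r = 0.20, 0.203 × 6.245 = 1.27, and Φ(-0.69) ≈ 24%.
- Joint model, approximately: SE = √[(1 − R²)/((n − 4)(1 − ρ²))], with R² = 2b²(1 + ρ) + b₃². Example at ρ = -0.5, b₃ = 0: R² = 0.16, SE = √(0.84/28.5) = 0.172, 0.4/0.172 = 2.33, and Φ(2.33 − 2.02) ≈ 62%. Simulation (6,000 runs per cell) gave 61.3%.

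| ρ | Simple r | Power, simple test | Power, joint model (simulated, b₃ = 0 to 0.2) |
|---|---|---|---|
| -0.5 | 0.20 | 24% | 61-65% |
| -0.2 | 0.32 | 54% | 77-80% |
| 0 | 0.40 | 75% | 82-84% |
| +0.2 | 0.48 | 90% | 83-86% |

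At +0.2 the simple test has more power, but its 0.48 overstates the factor's own effect of 0.40.

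**2. A factor with no own effect.** It correlates at ρ with a factor of effect 0.4, so its simple correlation is 0.4ρ.

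- |ρ| = 0.5: size of r is 0.20. Significant in about 25% of simulations with the simple test, and 4.3-5.2% in the joint model.
- |ρ| = 0.2: size of r is 0.08. Significant in 7.4-8.0%, against 4.5-5.3%.

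**3. Group tests in place of correlation.** True r = 0.4, three equal-sized systolic pressure groups (assumed), 40,000 runs.

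| n | Pearson | ANOVA | Kruskal-Wallis |
|---|---|---|---|
| 40 | 74% | 52% | 48% |
| 42 | 76% | 53% | 50% |
| 45 | 80% | 57% | 54% |

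**4. What a joint model can deliver.** At n = 42 the 95% interval for a standardised coefficient has a half-width of about 0.25-0.34. Power to show that two coefficients differ is as follows.

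| ρ | 0.4 vs 0.2 | 0.4 vs 0 |
|---|---|---|
| -0.5 | 22% | 65% |
| -0.2 | 20% | 54% |
| 0 | 17% | 46% |
| +0.2 | 15% | 40% |
| +0.5 | about 11-12% | 26% |

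**The case against.** The strongest reply is that the primary outcome asks only for a relationship, which the protocol's correlations can describe. The SAP's opening sentence names software and does not say its list of tests is complete, and the protocol, with the same date, still plans the correlations. That is fair. The SAP omission is an inconsistency between documents, and the missing joint analysis bears on the research question more than on the primary outcome as worded.

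A second objection concerns mediation. If volume acts partly through angiotensin II, the simple correlation reflects the total association and the adjusted coefficient only the direct part. Neither alone is relative importance. This stands as a caution on interpretation, and it is a reason to report both.

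Third, the large contrasts need a correlation of about 0.5 in size. At 0.2 false attribution is barely raised, and overlap between inflammation and the other two factors was not modelled. Equal thirds has no basis in the documents; several unequal splits gave ANOVA power of about 44-50%, so 53% is not specific to this trial. These points limit the figures but do not supply the missing analysis.

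Finally, even a joint model ranks factors poorly at this sample size and would probably be post hoc. That is correct, and it determines how the results should be presented.

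**Conclusion.** The concern holds. The omission is plain from the text: a comparative question about three factors, one-factor-at-a-time methods in the protocol, group tests only in the SAP, and no joint analysis in either.

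How much it matters depends on how strongly the factors are related in these patients, which the documents do not say. The loss is serious at a correlation near 0.5 in size. Near 0.2, false attribution is small; the power loss is still about 23 to 26 points at -0.2, and at +0.2 the simple test has the higher power. Followed as written, the plan can report which factors are associated with ambulatory pressure singly, but not what each adds given the others. This should be fixed; it does not invalidate the study. Confidence is high on the omission, while the magnitudes are illustrations under stated assumptions.

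**What to change.** 1. List the Pearson/Spearman correlations in the SAP as the analysis of the primary outcome, and keep the three pressure groups as descriptive.
2. Add to both documents one linear regression of continuous mean ambulatory systolic pressure on interdialytic weight gain, log2 angiotensin II and log2 TNF-alpha. Use NMLR in place of TNF-alpha as a sensitivity analysis. The protocol ranks neither marker and makes log2 conditional on non-normality, so both choices must be stated.
3. Report standardised coefficients and partial R-squared with 95% intervals beside the simple correlations. Say that adjusted coefficients exclude any effect acting through another factor.
4. Repeat with the night/day systolic ratio as outcome, since dipping is part of the working hypothesis.
5. Name the water factor as interdialytic weight gain in the conclusions, because bioimpedance was not obtained. If use of renin-angiotensin-blocking drugs can be taken from charts, add it as a sensitivity covariate only.
6. Date the change and label it exploratory or post hoc where data are already collected: the protocol's study dates end in June 2024 and both documents are dated 2025.
7. Present estimates, not a ranking, or reword the question as the association of each factor with ambulatory pressure, adjusted for the others.

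The cost is wording in two documents, two main regressions and a few sensitivity fits, with no new patients or procedures. The price is wide intervals and low power to show that one factor outranks another.

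### Secondary outcome 2 correlates cardiac output and vascular resistance with other variables without specifying any allowance for body size or vascular access, so a size or access effect could pass for a haemodynamic relation

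*Protocol*

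**What the plan says.** - **Measurement.** The protocol (Methods, Hemodynamic determinations) defines output as an absolute flow: "Cardiac output (systolic volume x heart frequency) will be determined by ultrasound doppler of the flow of the outlet of left ventricle". The General list under Methods says that output and central venous pressure, obtained 1–2 hours after dialysis, serve to calculate resistance. The formula and the pressure reading that enters it are not given.
- **Use.** Secondary outcome 2 is: "Evaluate the relationship between interdialytic weight gain, and other variables under study with hemodynamic parameters (systemic vascular resistance and cardiac output").
- **Method.** The protocol's Statistical Analysis section offers Pearson or Spearman correlation for relationships, with this criterion: "Two-tail p values <0.05 will be considered significant". It names no partial correlation, regression or covariate. The SAP describes only group comparisons and mentions neither correlations nor haemodynamic variables.
- **Size and access.** The Abstract says "Weight, blood pressure, dialysis characteristics will be recorded", without listing the dialysis characteristics. Access appears only as the sampling site: "venous side of the vascular access before the beginning of dialysis". No eligibility criterion concerns access type. Neither document mentions height, body surface area, cardiac index, resistance index, access type or access flow. The unit of interdialytic weight gain (kg or % of body weight) is not stated.
- **Numbers.** The Sample size section invites every eligible patient and states no effect size or power. Under Recruitment potential: "Our estimate is 40-45 patients from a total of 50-55 in the chronic hemodialysis program of the INCMNSZ".

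**The concern.** Two features of the measured flow have nothing to do with the physiology that secondary outcome 2 asks about.

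First, larger people have larger absolute output and hence, at the same pressure, lower calculated resistance. If larger people also gain more kilograms between sessions, output and weight gain will correlate through size alone. Weight gain is the one predictor that the outcome names.

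Second, outflow at the left ventricle includes any blood that passes directly from artery to vein through a fistula or graft. A patient with a catheter has no such flow. Calculated resistance is therefore lower with a fistula or graft, with no difference in arteriolar tone.

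An unadjusted correlation cannot separate either effect from a real relation. A significant result for this outcome could then be read as a mechanism when it reflects build or access.

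**Working it through.** The plan states no power or effect size, so there is no figure of its own to reproduce. From the documents: two-sided 0.05, n = 40 to 45, unadjusted correlation. Every correlation, flow and pressure below is an assumption.

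**1. What the study can detect.** The critical value is r = t/√(n−2+t²), with t the 97.5% point on n−2 degrees of freedom: 0.312 at n = 40 and 0.294 at n = 45. The correlation detectable with 80% power is tanh[(1.960+0.842)/√(n−3)]: 0.431 and 0.407.

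**2. Body-size route.** Let a be the correlation of size with output and b that of size with weight gain, with no other link. The induced correlation is ρ = a·b. The rejection probability is 1−Φ(1.960−m)+Φ(−1.960−m), with m = atanh(ρ)·√(n−3).

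| a | b | ρ | n = 40 | n = 45 |
|---|---|---|---|---|
| 0.3 | 0.3 | 0.09 | 8.5% | 9.0% |
| 0.3 | 0.5 | 0.15 | 15.1% | 16.5% |
| 0.5 | 0.5 | 0.25 | 34.2% | 38.0% |

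For the last row at n = 40: atanh(0.25) = 0.255; m = 0.255 × √37 = 1.55; 1−Φ(0.41) = 0.34.

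A simulation of 10,000 replicates used systemic flow 5 ± 1 L/min, access flow 1.0 ± 0.5 L/min unrelated to weight gain, mean arterial pressure 100 ± 13 mmHg and central venous pressure 8 ± 3 mmHg. For a = b = 0.3 and a = b = 0.5, the false-positive rates were about 8% and 28–32% for output, and about 7% and 19–22% for resistance. Partial correlation on size brought output against weight gain back to about 5% (4.7–5.4% across the size scenarios run).

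**3. Effect of access flow on resistance.** Resistance = 80 × (mean pressure − central venous pressure)/output. With systemic flow 5.0 L/min, mean pressure 100 and central venous pressure 8 mmHg:
- no access flow: 80 × 92/5.0 = 1472 dyn·s/cm⁵
- 0.6 L/min: 80 × 92/5.6 = 1314 (−11%)
- 1.0 L/min: 80 × 92/6.0 = 1227 (−17%)
- 1.5 L/min: 80 × 92/6.5 = 1132 (−23%)

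**4. When that becomes bias.** In the same simulation without a size effect:

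| Access flow vs weight gain | Output, false positives | Resistance, false positives |
|---|---|---|
| Independent | about 5% | about 5% |
| Correlation 0.3 | 12–13% | 9–10% |
| Correlation 0.5 | 27–30% | 17–20% |

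Adjusting for access flow itself restored about 5% for output. Where size was the confounder, adjusting for access flow alone left output false positives at 8.5–66% over the size scenarios run (up to a = 0.7, b = 0.5), so one covariate does not stand in for the other.

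**5. A hypothetical link with inflammation.** Suppose 30–50% of patients have catheters, an inflammatory marker is 0.5–1.0 SD higher in them, access flow in the rest is 0.6–1.5 L/min, systemic flow has 15% spread and the pressure gradient is 92 ± 12 mmHg. The spurious correlation of the marker with resistance is then about 0.06 to 0.26. With 25% flow spread and a gradient of 92 ± 15 it is 0.04 to 0.20. By the formula in step 2, r = 0.06 means 6.5–6.8% false positives and r = 0.26 means 37–41%.

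**The case against.** The case against making much of this is substantial.

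- **Raw totals are not a stated commitment.** The resistance formula is not given and indexing is not ruled out. This stands: the fair statement is that no indexing or adjustment is specified.
- **The access route rests on facts outside the documents.** They give neither the access mix nor any difference in inflammation by access, and the inclusion criteria require a stable month without evidence of infection, which closes one obvious path from catheter to inflammation. If nearly everyone has the same type of access, the contrast largely disappears. This stands: the route is conditional, and the upper figure in step 5 needs every unfavourable assumption at once.
- **The working hypothesis is not at stake.** A reader might infer that the study would report inflammation rising with vascular resistance and so falsely confirm its own hypothesis. The documents do not support that. The hypothesis concerns severity of hypertension and absent nocturnal dipping; resistance enters only through secondary outcome 2. The primary outcome uses neither output nor resistance.
- **Dividing by body surface area can over-correct.** It removes size exactly only if output is proportional to surface area. In a simulation with no true link, 10% spread in surface area, 15% residual spread in output and a size–gain correlation of 0.44, output scaling as surface area to the power 0.6 gave r = +0.16 raw and −0.11 indexed; to the power 0.3, +0.09 and −0.18. This stands, and is why size should enter as a covariate and the indices be reported only alongside.

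None of this closes the body-size route while the weight-gain unit is unstated and the only method is an unadjusted correlation.

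**Conclusion.** The concern holds in a limited form. As written, secondary outcome 2 cannot separate a haemodynamic relation from body size or, where access differs between patients, from access flow.

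The body-size route is the stronger. With assumed correlations of 0.3 to 0.5 on each side, the false-positive rate for output against weight gain is about 9% to 38% at n = 40 to 45. It would be weaker if weight gain is expressed as a percentage of body weight. The access route creates bias only for variables that differ by access type or flow. Otherwise it adds noise, which still matters in a study that needs r of about 0.41 to 0.43 for 80% power.

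The documents fix none of these magnitudes. With the primary outcome untouched and the correlations exploratory, this is a cheap improvement of low to moderate priority.

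**What to change.** For secondary outcome 2, specify in the SAP:

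1. Partial (or partial rank) correlation, or regression, as the main analysis, with two covariates: body size and access type (fistula or graft versus catheter). Use body surface area for size, or recorded weight if height is unavailable.
2. Cardiac index and resistance index reported beside the raw values, not in place of the size covariate.
3. The unadjusted correlations reported as secondary.
4. The resistance formula with the pressure reading it uses, and the unit of interdialytic weight gain.

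**Cost.** About two degrees of freedom in 40 to 45 patients, so further covariates should be few. No new procedure on patients is needed. Height is never mentioned, and the protocol does not say that the recorded dialysis characteristics include access type, so both may have to be retrieved from dialysis or clinical records. A two-level access term leaves differences in flow among fistula and graft patients unadjusted; the report should say so.
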